### 11.3 Exploratory Analyses

Since the within-household correlation is expected to be small, the change and percent change from Baseline in the number of treatable MC at Weeks 2, 8 and 12 will be analyzed using a repeated measures mixed model for the respective visits with the same covariates as the primary model together with visits and treatment by visit; an unstructured covariance matrix will be utilized. If the calculation of the percent change from baseline is influenced by outliers with calculated values  $>100\%$ , then the influence of outliers will be avoided for analysis by censoring them so that all values were in the range of  $-100\%$  to  $100\%$ . If the model fails to converge, then other correlation structures will be explored.

The exploratory endpoints based on the proportion of subjects achieving complete clearance (at Weeks 2 and 4) or 75% (at Weeks 2, 4, 8, and 12) or 90% (at Weeks 2, 4, and 8) reductions will be analyzed in the same manner as the primary endpoint.

Likewise, the proportion of subjects achieving a lesion count of 0 or 1 of all treatable MC at Weeks 2, 4 and 8 will be analyzed in the same manner as the primary endpoint.

Since the within-household correlation is expected to be small and time to first complete clearance of all MC is exploratory, it will be analyzed using Kaplan-Meier methods. The number and percentage of subjects achieving complete clearance, number and percentage of censored subjects, and Kaplan-Meier estimates of first quartile, median, and third quartile will be summarized by treatment group. Differences in Kaplan-Meier curves between the treatments will be tested for significance using a stratified log-rank test.

The proportion of subjects who have a recurrence of MC after the first visit at which complete clearance was observed will be summarized.

The subject-reported spread of MC to household members not in the study will be summarized descriptively including a breakdown of whether or not there was any spread and then a breakdown of the amount of spread within the household at each visit at the household level.

A shift table comparing the baseline global severity assessment to each scheduled postbaseline assessment will be presented by subject and investigator. The Investigator and Subject Global Impression of change will be summarized descriptively.

Separate plots of the cumulative distribution function of the percentage change from Baseline in lesion count at Week 12 across each of the scores for the Subject Global Impression of Change and the Subject Global Severity Assessment will be presented for all subjects. These plots will also be replicated separately for subjects in the SB206 10.3% QD group and for subjects in the Vehicle group.

A plot comparing Improved vs Not Improved, including the correlation between percentage change from Baseline in lesion count at Week 12 and improvement category, in each treatment group and overall will be presented separately for the Subject Global Impression of Change at Week 12. Improved will be defined as selecting either 'Very Much Improved', 'Much Improved', or 'Minimally Improved' and not improved as selecting either 'No Change', 'Minimally Worse', 'Much Worse', or 'Very Much Worse'.

A plot comparing No Severity vs Severity, including the correlation between percentage change from Baseline in lesion count at Week 12 and severity category, in each treatment group and overall will be presented separately for the Subject Global Severity Assessment at Week 12. No Severity will be defined as having a response of 'None' and Severity will be defined as having a response of 'Mild', 'Moderate', 'Severe', or 'Very Severe'.

The correlation between the following will be presented.

- Baseline lesion count and Subject Global Severity Assessment at Baseline
- Baseline lesion count and Subject Global Severity Assessment at Week 12
- Baseline lesion count and Subject Global Impression of Change at Week 12
- Baseline lesion count and Investigator Global Severity Assessment at Baseline
- Baseline lesion count and Investigator Global Severity Assessment at Week 12
- Baseline lesion count and Investigator Global Impression of Change at Week 12

The following efficacy endpoints will be descriptively summarized for the Improved vs Not Improved categories of the Subject Global Impression of Change at Week 12.

- Proportion of subjects with complete clearance of all treatable MC at Week 12.
- Proportion of subjects achieving a lesion count of 0 or 1 of all treatable MC at Week 12.
- Proportion of subjects achieving at least a 90% reduction from Baseline in the number of all treatable MC at Week 12.
- Proportion of subjects achieving at least a 75% reduction from Baseline in the number of all treatable MC at Week 12.
- Percent change from Baseline in the number of treatable MC at Week 12.

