The primary endpoint for these studies was the proportion of subjects in the ITT population with complete clearance of all treatable molluscum lesions at Week 12. Subjects with missing Week 12 lesion count data were counted as non-responders. In [NI-MC301](#), 25.8% achieved complete clearance at Week 12 with SB206 and 21.6% achieved complete clearance at Week 12 with Vehicle; 30.0% of subjects on SB206 and 20.3% of subjects on Vehicle in [NI-MC302](#) achieved complete clearance at Week 12. Although the primary analysis alone did not achieve statistical significance at the 0.05 level in either study, there is a positive trend within and across both studies. An integrated analysis of the primary endpoint for the combined studies was performed. This post hoc analysis shows a continued trend of effectiveness by achieving statistical significance with a complete clearance of 27.9% for SB206 and 20.9% for vehicle (p= 0.0387). Based on these results, an additional phase 3 study, NI-MC304, is being conducted with SB206.

Topical formulations of berdazimer sodium at concentrations ranging from 1-16% have been studied. Over 1900 healthy volunteers or subjects with MC, acne, genital warts, atopic dermatitis, psoriasis, or tinea pedis have been exposed to Vehicle and over 3,400 exposed to berdazimer sodium as of January 31, 2020. In clinical studies completed to date, topical application of berdazimer sodium has generally been well-tolerated with no safety concerns identified. Note that description of the concentration of SB products used nominal numbers based on percent berdazimer sodium historically. Novan has updated the naming convention to use percent berdazimer. Therefore, SB206 12% (nominal berdazimer sodium) is the same admixture formulation as SB206 10.3% (berdazimer). In this protocol, the nominal berdazimer sodium numbers remain in historical studies.

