## 5. DETERMINATION OF SAMPLE SIZE

Approximately 850 subjects, 6 months of age and older, with a minimum of 3 and a maximum of 70 MC lesions at Baseline will be randomized in a 1:1 (active:vehicle) scheme. The sample size assumptions for this study were informed by the integration of the completed phase 3 studies [NI-MC301](#) and [NI-MC302](#). Multiple replications of simulated random sampling of the integrated NI-MC301 and NI-MC302 data was performed to ensure the sample size assumptions align with the proposed design of NI-MC304. This includes the 1:1 ratio (active:vehicle) and the percentages observed in NI-MC301 and NI-MC302 for each stratum of each of the stratification factors: investigator type, number of randomized subjects per household, and baseline BOTE score that are planned for NI-MC304.

The analysis of the proportion of subjects with complete response of all treatable MC at Week 12 within the Intent-to-Treat (ITT) Population of the multiple replications of simulated random sampled integrated data yields rates of 20% for vehicle and 29.5% for SB206 10.3% QD with the covariate-adjusted treatment difference was 9.5%. A sample size of 850 subjects (425 subjects in the SB206 10.3% QD group and 425 subjects in the vehicle group) will provide 90% power for a 2-sided alpha test of size 0.05 to detect an absolute difference of 9.5% when the vehicle response rate is 20%.

Simulations were performed with 10,000 replications to confirm the accuracy of these power estimates (i.e., true power and simulation based estimate of power) and to provide simulated median, 10% percentile and lowest detectable treatment difference estimates for a sample size of 850 subjects.

At the two-sided  $\alpha=0.05$  level, the median detectable treatment difference is approximately 9.9% with a simulation based estimated power of 88%. The tenth percentile for detectable treatment difference is 7.1%, thus approximately 90% of the simulations with two-sided  $p < 0.05$

produced an estimated treatment difference exceeding 7.1%. The lowest detectable treatment difference is 5.7%.

At two-sided alpha levels  $<0.05$ , for example,  $p=0.025$  level, the median detectable treatment difference is approximately 10.2% with a simulation based estimated power of 82%. The tenth percentile for detectable treatment difference is 7.7% and a lowest detectable difference of 6.5%.

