14.3.1.6	Summary of Treatment-Emergent Adverse Events Leading to Study Drug Discontinuation by System Organ Class and Preferred Term	Safety

Table Number	Table Title	Analysis Population
14.3.1.7	Summary of Treatment-Emergent Adverse Events Leading to Death by System Organ Class and Preferred Term	Safety
14.3.1.8.1	Summary of Treatment-Emergent Adverse Events Leading to Study Discontinuation by System Organ Class and Preferred Term	Safety
14.3.1.8.2	Summary of Post Treatment Adverse Events Leading to Study Discontinuation by System Organ Class and Preferred Term	Safety
14.3.1.9	Summary of Transient Treatment-Emergent Adverse Events by System Organ Class and Preferred Term	Safety
14.3.2	Listings of deaths, other serious and significant adverse events	
14.3.2.1	Listing of Serious Adverse Events	Safety
14.3.2.2	Listing of Adverse Events Leading to Study Drug Discontinuation	Safety
14.3.2.3	Listing of Deaths	Safety
14.3.6	Other safety data	
14.3.6.1.1	Summary of Local Skin Reaction (LSR) Composite Score by Visit	Safety
14.3.6.1.2	Summary of Local Skin Reaction (LSR) Score Results by Visit	Safety
14.3.6.1.3	Shift Summary of Local Skin Reaction (LSR) Score Results by Visit	Safety
14.3.6.1.4	Summary of Local Skin Reaction (LSR) Composite Score by Dichotomized Baseline BOTE Score and Visit	Safety
14.3.6.1.5	Summary of Local Skin Reaction (LSR) Individual Score by Dichotomized Baseline BOTE Score and Visit	Safety
14.3.6.2	Summary of Events of Special Interest	Safety
14.3.6.3	Summary of Physical Examination Findings	Safety
14.3.6.4	Summary of Scarring and Keloid by Visit	Safety
14.3.6.5	Summary of Patch Testing Results	Safety

Figure Number	Figure Title	Analysis Population
14.2.1.5	Forest Plot: Odds Ratio (95% CI) of the Proportion of Subjects with Complete Clearance at Week 12	ITT
14.2.2.4.2	Percent Change from Baseline in Lesion Count over Time by Treatment Group	ITT
14.2.3.4.2	Mean Change from Baseline in Lesion Count over Time by Treatment Group	ITT
14.2.3.6.2	Kaplan-Meier Plot of Time to Complete Clearance (Days) from Start of Dosing	ITT
14.2.3.9.2	Cumulative Distribution Function Plot Across Subject Global Severity Assessment Responses	ITT
14.2.3.9.3	Cumulative Distribution Function Plot by Subject Global Severity Assessment Severity Category	ITT
14.2.3.10.2	Cumulative Distribution Function Plot Across Subject Global Impression of Change Responses	ITT

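### Kaplan-Meier median and third quartile for time to clearance are not meaningfully estimable with follow-up to Week 12 and 20-30% expected clearance, and no effect size is planned in their place

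*SAP*

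**What the plan says.** SAP 11.3 analyses time to first complete clearance by Kaplan-Meier. It plans, by arm, the number and percentage cleared, the number and percentage censored, and quartiles: "Kaplan-Meier estimates of first quartile, median, and third quartile will be summarized by treatment group". Protocol 10.3.6 has the same sentence. The SAP then adds a test: "Differences in Kaplan-Meier curves between the treatments will be tested for significance using a stratified log-rank test". SAP Appendix C lists Table 14.2.3.6.1 for the estimates and Figure 14.2.3.6.2, "Kaplan-Meier Plot of Time to Complete Clearance (Days) from Start of Dosing".

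SAP 10.1 runs the clock from first dose to the date of first clearance, and censors everyone else at the date of the last lesion count. These are actual dates. Protocol 7.2.6 states that no lesion count is made after Week 12, and the schedule of assessments puts that visit at Day 85 ±5.

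On expected rates, Protocol 2.1 reports for the two earlier phase 3 studies combined "a complete clearance of 27.9% for SB206 and 20.9% for vehicle", and says of the rule behind those figures: "Subjects with missing Week 12 lesion count data were counted as non-responders". SAP 5 plans on simulated sampling that "yields rates of 20% for vehicle and 29.5% for SB206 10.3% QD".

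**The concern.** A Kaplan-Meier quartile exists only if the curve gets that far. Observation ends at Week 12, when fewer than a third of subjects are expected to have cleared, so two of the three planned quartiles ask for something the data should not contain. They can fail in two ways. On nominal visit days the table shows them as not reached. On actual dates the last few subjects in the Week 12 window can drag the curve past 50% and print a number that looks like a median.

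Protocol 2.1.4.3 says Kaplan-Meier analysis in the earlier studies showed a shorter time to clearance. If a similar statement is wanted from this trial, the plan supplies a p-value and a picture but no estimate of how much sooner clearance occurs.

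**Working it through.** **1. The plan's own figure.** The documents give no sample size or power for time to clearance. The only stated figure is 90% power for the primary comparison (425 per arm, 20% vs 29.5%, two-sided 0.05). SE = √(0.20×0.80/425 + 0.295×0.705/425) = 0.0294; Φ(0.095/0.0294 − 1.96) = 89.8% (89.6% with pooled variance). It reproduces.

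**2. Expected clearance on the Kaplan-Meier scale.** The quoted rates count missing as failure, whereas Kaplan-Meier censors.
- Discontinuation (Protocol 2.1): 15.3% of 352 and 17.2% of 355, so d = (0.153×352 + 0.172×355)/707 = 16.3%.
- Rough conversion p/(1−d): planning rates 0.295 → 35.2% and 0.20 → 23.9%; combined earlier rates 0.279 → 33.3% and 0.209 → 25.0%.
- Shortfall to 50% at the planning rates: 14.8 points for SB206, 26.1 for vehicle. It could be made up only by subjects who cleared first and had lesions again at Week 12. The documents give no recurrence rate.

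**3. First quartile.** Week 8 clearance (Protocol 2.1.4.3) was 15.3% and 13.9% on SB206, and 10.3% and 5.9% on vehicle. Weighted by approximate arm sizes this is 14.6% and 8.1%, or 17.4% and 9.7% after dividing by 1−d. Both are below 25%, so on nominal days the first quartile is Day 85 or not reached. The chance that the crude Week 12 proportion is at least 25% with 425 per arm is 98% for SB206 at 29.5% and 0.5% for vehicle at 20%.

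**4. Actual dates.** Assume Week 12 visits are uniform over Days 80-90. Let h be the chance of clearing at Week 12 if uncleared at Week 8. On a day when m elevenths of the subjects remain to be seen, the Kaplan-Meier factor is 1 − h/m. The whole window contributes the product over m = 1 to 11.
- SB206, dropout-corrected: h = (0.3523 − 0.1743)/(1 − 0.1743) = 0.2155; product 0.501; final survival 0.8257×0.501 = 0.413. The curve ends at 58.7%, not 35.2%. It is at 47.3% on Day 89 and passes 50% on Day 90.
- SB206, uncorrected: h = (0.295 − 0.146)/(1 − 0.146) = 0.1745; product 0.575; the curve ends at 50.9%, not 29.5%.
- Vehicle, uncorrected: h = (0.20 − 0.081)/(1 − 0.081) = 0.1295; product 0.667; the curve ends at 38.7%, not 20%.

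**5. Simulation.** 300 trials of 425 per arm, 16.3% dropout spread evenly over the earlier visits. Week 2 and Week 4 clearance are assumed (1% / 0.5% and 4.5% / 2%); Week 8 is as in step 3. Entries are SB206 / vehicle; the last three columns give the share of trials in which the quartile was printed.

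| Rates | Visit days | Final curve | Q1 | Median | Q3 |
|---|---|---|---|---|---|
| Planning | nominal | 29.8% / 19.8% | 97% / 0% | 0% / 0% | 0% / 0% |
| Planning | SD 2 days | 60.8% / 46.8% | 100% / 100% | 79% / 33% | 12% / 3% |
| Planning | uniform | 50.5% / 38.6% | 100% / 100% | 55% / 3% | 0% / 0% |
| Dropout-corrected | nominal | 35.3% / 23.8% | 100% / 28% | 0% / 0% | 0% / 0% |
| Dropout-corrected | SD 2 days | 68.0% / 53.2% | 100% / 100% | 98% / 57% | 24% / 4% |
| Dropout-corrected | uniform | 58.7% / 44.9% | 100% / 100% | 95% / 18% | 0% / 0% |

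When the SB206 median printed, it typically fell around Day 88-90. The uniform rows agree with step 4.

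**6. Log-rank test.** With proportional hazards, HR = ln(1−0.295)/ln(1−0.20) = 1.57 and events = 425×(0.295+0.20) = 210, giving 90% power (unstratified simulations: 89-95%). At the combined earlier rates, HR 1.40 and 207 events give 67%.

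**The case against.** Two stronger readings are tempting. The documents support neither.

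A reader might infer that the summary gives no contrast between arms. It does. The same SAP paragraph plans counts and percentages cleared by arm and a stratified log-rank test, which has useful power (step 6), and Appendix C adds the plot. SB206 should reach its first quartile, and on nominal days reached against not reached is itself a difference, though one without a size. SAP 11.1 to 11.3 also analyse complete clearance at Weeks 2, 4, 8 and 12 with odds ratios and predicted proportions. Those measure status at a visit with missing counted as failure, not cumulative first clearance. They overlap with what is missing here but do not replace it.

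A reader might also infer that the median and third quartile are certain to be blank. That does not follow. The quoted rates are Week 12 status, while the endpoint keeps a first clearance even if lesions return. The discontinuation rates are for the whole study and need not all precede Week 12. Step 5 shows that a median may well print. This does not rescue it: a median produced by the last days of a visit window, when about a third have cleared, misleads more than a blank entry.

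It is fair to add that not reached is a normal table entry, and that the sentence on faster clearance in Protocol 2.1.4.3 is background, not a planned claim.

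**Conclusion.** The point holds for the median and third quartile, and for the missing effect size. At 20-30% expected clearance (about 24-35% with dropouts censored), neither quartile can be meaningfully estimated in either arm. They are not reached on nominal days. On actual dates an artefact SB206 median appears in 55-98% of simulated trials and a vehicle one in 3-57%. No hazard ratio, cumulative clearance estimate with CI, or restricted mean difference is specified for time to clearance.

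This rests on clearance close to the planning or earlier rates, limited transient clearance before Week 12, dropouts who would have cleared like those who stayed, and the assumed early clearance and visit-day spread. The last affects how often the artefact appears, not whether the mechanism exists.

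Importance is low. The endpoint is exploratory and outside the fixed-sequence testing of SAP 10.7. Nothing here touches the primary or secondary conclusions.

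**What to change.** Before the Week 12 unblinding described in SAP 6, amend SAP 11.3, Protocol 10.3.6 and the shell for Table 14.2.3.6.1, and align the time definition in SAP 10.1:

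- Assign event and censoring times to nominal analysis visits (Days 15, 29, 57 and 85), or use an interval-censored estimator.
- Replace the median and third quartile with cumulative clearance at Weeks 4, 8 and 12 by arm, with 95% CIs and the between-arm difference at each.
- Add the between-arm difference in restricted mean time to clearance to nominal Day 85.
- Keep the counts, the log-rank test and the plot.

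The first item is essential. With actual dates, a Day 85 cut-off would miss Week 12 clearances seen on Days 86-90, which is 5 of 11 days (about 45%) if visits are uniform over the window.

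One limit needs a footnote. On a nominal grid a step at Day 85 adds no area before Day 85, so the restricted mean reflects only clearances up to Week 8. The Week 8 difference of 14.6 − 8.1 = 6.5 points contributes 0.065×28 = 1.8 days. It should be read beside the Week 12 cumulative estimate.

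The cost is minor SAP, protocol and table-shell rework, and some loss of exact visit-day information. No new data are needed.

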## 12. OTHER ANALYSES

The following analyses of BOTE vs lesion count will be presented:

- Percent change from Baseline in the number of treatable MC at each visit in relation to the Baseline BOTE score comparing No Inflammation vs Inflammation within each treatment group through a repeated measures mixed model with number of randomly assigned subjects in household (1 subject vs 2 subjects), investigator type (dermatologist

vs other), BOTE score at Baseline (no inflammation [BOTE=0] vs mild/moderate/severe/very severe inflammation [BOTE $\geq$ 1]), BOTE score at Baseline by visit interaction, age, and baseline lesion count as covariates with a compound symmetry covariance matrix.

- Percent change from Baseline in the number of treatable MC at Week 12 in relation to the highest post-baseline BOTE score during treatment will be summarized descriptively.
- Percent change from Baseline in the number of treatable MC at Week 12 in relation to the highest BOTE score at any visit (including Baseline) will be summarized descriptively.
- Percent change from Baseline in the number of treatable MC at each visit in relation to the BOTE score at Week 2 will be summarized descriptively.

In these analyses, the BOTE scores will be analyzed in the ITT Population as follows:

1. Dichotomized:
  - a. Score of 0: No Inflammation
  - b. Score of 1, 2, 3, or 4: Mild to Very Severe

A shift table comparing the baseline BOTE score to each scheduled post-baseline assessment will be presented for the ITT Population.

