## 11.2 Secondary Efficacy Analyses

The secondary endpoints of the proportion of subjects achieving a lesion count of 0 or 1 of all treatable MC at Week 12, proportion of subjects achieving at least a 90% reduction from Baseline in the number of all treatable MC at Week 12, and the proportion of subjects with complete clearance of all treatable MC at Week 8 will be analyzed in the same manner as the primary endpoint.

Since the within-household correlation is expected to be small, the percent change from Baseline in the number of all treatable MC at Week 4 will be analyzed using a repeated measures mixed model for the respective visits with the same covariates as the primary model together with visits and treatment by visit interaction; an unstructured covariance matrix will be utilized. If the calculation of the percent change from baseline is influenced by outliers with calculated values >100%, then the influence of outliers will be avoided for analysis by censoring them so that all values were in the range of -100% to 100%. If the model fails to converge, then other correlation structures will be explored.

A sensitivity analysis using the PP Population will be provided for the proportion of subjects achieving a lesion count of 0 or 1 of all treatable MC at Week 12 and the proportion of subjects achieving at least a 90% reduction from Baseline in the number of all treatable MC at Week 12.

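### The baseline-BOTE model in SAP 12 specifies compound symmetry where SAP 11.2 and 11.3 use an unstructured matrix for the same outcome, so its visit-specific intervals may be miscalibrated if variance differs by visit

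*SAP*

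**What the plan says.** The first bullet of SAP 12 (Other Analyses) models "Percent change from Baseline in the number of treatable MC at each visit in relation to the Baseline BOTE score", contrasting no inflammation with any inflammation inside each treatment group. The terms include a baseline-BOTE-by-visit interaction, "age, and baseline lesion count as covariates with a compound symmetry covariance matrix". The interaction with visit means that the model's output is a BOTE contrast at each visit. The section gives no rationale for the structure, no rule for non-convergence and no robust standard errors.

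For percent change at Week 4, SAP 11.2 specifies "treatment by visit interaction; an unstructured covariance matrix will be utilized", and adds: "If the model fails to converge, then other correlation structures will be explored". For change and percent change at Weeks 2, 8 and 12, SAP 11.3 specifies "treatment by visit; an unstructured covariance matrix will be utilized", with the same convergence rule. Both sections also allow extreme percent changes to be limited to the range −100% to 100%. SAP 12 does not repeat that limit.

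Protocol 10.3.5 leaves BOTE-versus-lesion analyses as optional exploration and sets no covariance structure. SAP 12 commits to presenting this one, and SAP Appendix C gives it Table 14.2.3.12.1.

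**The concern.** Compound symmetry assumes the same residual variance at Weeks 2, 4, 8 and 12 and the same correlation between every pair of visits. The standard error of the BOTE contrast at any visit is then built on a pooled variance. Where the true spread exceeds the pooled value, the interval is too narrow and the 0.05 test too liberal. Where it falls short, the interval is too wide.

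Two facts in the protocol make unequal spread plausible. Section 2.1.2.1 says that a rise in lesion numbers early in treatment is common. Section 2.1.4.3 shows the share of subjects at exactly −100% (complete clearance) growing between Week 8 and Week 12:

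- NI-MC301: SB206 15.3% to 25.8%, vehicle 10.3% to 21.6%
- NI-MC302: SB206 13.9% to 30.0%, vehicle 5.9% to 20.3%

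The distribution therefore changes shape over the visits that the model pools. At stake is whether the visit-by-visit BOTE associations in one exploratory table carry the error rates that they appear to carry.

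**Working it through.** The plan states no figure for this model, so there is none to reproduce. Its one power figure (90% for the primary endpoint, 425 per arm) recomputes to 89.6% and has no bearing here.

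**Inputs from the documents.** Post-baseline counts at Weeks 2, 4, 8 and 12 (SAP 10.1); 425 subjects per arm (SAP 5); two-sided 0.05 (SAP 6); discontinuation of 15.3% and 17.2% in the two earlier phase 3 studies (Protocol 2.1), taken as 16%.

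**Assumed, because the documents do not give them.** SDs of percent change at each visit, correlations between visits, and 30% of subjects with baseline BOTE of 1 or more.

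**Step 1, parameters.** With four visits, compound symmetry has 2 covariance parameters and unstructured has 4 × 5 / 2 = 10. The difference is 8.

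**Step 2, analytic effect with complete data.** Pooled SD = √(mean of the four variances). Ratio of reported to true standard error at a visit = pooled SD / SD at that visit. Coverage = 2Φ(1.96 × ratio) − 1.

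Example, SDs 35/40/45/50: √[(1225 + 1600 + 2025 + 2500)/4] = √1837.5 = 42.9. At Week 12 the ratio is 42.9/50 = 0.857, and coverage is 2Φ(1.68) − 1 = 0.907.

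| Assumed SDs, Weeks 2/4/8/12 | Pooled SD | SE ratio by visit | Coverage of 95% interval by visit |
|---|---|---|---|
| 45/45/45/45 | 45.0 | 1.00 throughout | 95% throughout |
| 35/40/45/50 | 42.9 | 1.22/1.07/0.95/0.86 | 98/96/94/91% |
| 30/40/50/60 | 46.4 | 1.55/1.16/0.93/0.77 | 99.8/98/93/87% |
| 60/50/45/40 | 49.3 | 0.82/0.99/1.10/1.23 | 89/95/97/98% |

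**Step 3, simulation.** 500 REML fits per scenario: one arm of 425, 16% monotone dropout, and correlation either constant at 0.6 or decaying as 0.93 to the power of the gap in weeks. At 95% coverage the Monte Carlo standard error is √(0.95 × 0.05/500) = 1.0 point.

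- Equal SDs, either correlation pattern: compound symmetry covered 93–96%, in line with unstructured.
- SDs 35 to 50, decaying correlation: compound symmetry covered 90% at Week 12; unstructured covered 96%.
- SDs 30 to 60, decaying correlation: compound symmetry covered 100/98/91/84% across the visits; unstructured covered 92–93%. Type I error of the BOTE-by-visit test was 10.8% against 5.4%.
- SDs 30 to 60, constant correlation: compound symmetry covered 87% at Week 12. Type I error of the interaction test was 6.2% under both structures.

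Across all scenarios unstructured covered 92–96% at every visit. The equal-SD runs show that the common-correlation assumption alone does almost no damage to visit-specific intervals; unequal variance does it.

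**The case against.** A reader might infer that the intervals in this table are simply unreliable, and that false BOTE associations will appear at late visits. The documents support neither. No visit-specific SD is given, and with equal SDs compound symmetry is adequate. Nor is the direction known. Baseline counts can be as low as 3 (Protocol 5.2), so going from 3 to 9 lesions is a change of +200%, and early increases could make Week 2 the most variable visit. The too-narrow interval would then be at Week 2, and the Week 12 interval would be conservative. A growing mass at −100% can widen or shrink the spread, depending on the rest of the distribution.

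Nor does choosing an unstructured matrix in SAP 11.2 concede that variances differ; it only avoids assuming that they are equal. The models also serve different ends. SAP 11.2 compares randomised arms for an endpoint in the testing sequence, while SAP 12 compares non-randomised BOTE groups within an arm. A simpler structure for a subsidiary model can be defended.

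The heavier scenario is at the high end if the −100% to 100% limit were carried over: a uniform spread over that whole range has an SD of 200/√12 = 57.7, against the 60 assumed at Week 12.

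All of this stands, and it makes the point conditional and minor. It does not explain why the same outcome gets a more restrictive variance assumption without comment when the more general one is easily fitted.

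**Conclusion.** The inconsistency between SAP 12 and SAP 11.2/11.3 is in the text and is unexplained. Its consequence is conditional on variance differing by visit, which is plausible but not shown. Under the assumed SDs, the worst-affected visit has coverage of about 91% (35 rising to 50), 84–87% (30 rising to 60) or 89% (60 falling to 40, at Week 2), and there is no loss when SDs are equal. The 84% is a simulated value from runs in which unstructured itself covered 92–93%, so a little of that shortfall is simulation noise.

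The analysis lies outside the fixed testing sequence of SAP 10.7, so no primary or secondary conclusion is affected. This is a cheap improvement.

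**What to change.** In SAP 12, first bullet, replace compound symmetry with an unstructured covariance matrix, as in SAP 11.2. Pre-specify that if the model does not converge, compound symmetry will be used with empirical (sandwich) standard errors. If the sponsor prefers to keep compound symmetry, it should give the reason and use the empirical standard errors from the start. The same edit can say whether the −100% to 100% limit applies to this model.

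The cost is one line of SAP text and one line of code. The downside is 8 more covariance parameters, which about 425 subjects per arm and four visits can support. Unstructured contains compound symmetry as a special case, and in the equal-SD simulations its coverage was essentially the same, so little is given up if the variances turn out to be equal.
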